11.0 SAFETY ANALYSES

The safety analyses will be performed for the OL safety, OL SFU and DB safety populations. The summarization will be overall for the OLTP in the OL safety population and OL SFU period in the OL SFU population, and by treatment group for the DB period and the DB SFU period in the DB safety population. The summarization for the OLTP will use the OL safety population as the denominator. The summarization for the DBTP will use the DB safety population as the denominator. The summarization for the OL SFU period or DB SFU period will use the OL SFU population or the DB safety population as the denominator respectively.

Safety parameters will include adverse events (AEs), clinical laboratory parameters, vital signs, Electrocardiographic (ECG) parameters, ophthalmological parameters, Columbia–Suicide Severity Rating Scale (C-SSRS), and EPS scales, including Abnormal Involuntary Movement Scale (AIMS), Barnes Akathisia Rating Scale (BARS), and Simpson-Angus Scale (SAS).

For each safety parameter, the last assessment made before the first dose of OL IP will be used as the baseline for all analyses of that safety parameter, unless stated otherwise. Continuous variables will be summarized by number of patients and mean, SD, median, minimum, and maximum values. Categorical variables will be summarized by number and percentage of patients.

The derived visits in the DBTP will use the same strategy as described in Section 10.0. The detailed week mapping windows is provided in Section 16.1.

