7.1.4 Open-label Safety-Follow-up Population

The open-label safety-follow-up (OL SFU) population will consist of patients in the OL safety population who were not randomized.

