6.4 OPEN-LABEL SAFETY-FOLLOW-UP POPULATION

The OL SFU population will consist of patients in the OL safety population who were not randomized and completed at least one visit in the SFU period.

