6.6 DOUBLE-BLIND SAFETY POPULATION

The DB safety population will consist of all patients in the randomized population who took at least 1 dose of DB IP.

Patients will be included in the treatment group corresponding to the DB IP they actually received regardless of the treatment they were randomized to.

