6.7 DOUBLE-BLIND INTENT-TO-TREAT POPULATION

The DB ITT population will consist of all patients who took at least 1 dose of DB IP and had at least 1 post-randomization assessment of the PANSS or CGI-S scores during the DBTP of the study.

Patients will be included in the randomized treatment group for the DB ITT population.

7.0**STUDY PATIENTS****7.1****PATIENT DISPOSITION**

The OLTP starts with the first dose of OLTP and ends with one of the following: the last scheduled assessment at the Visit 13/end of OLTP (Week 18) or early termination (ET) before Visit 13 (Week 18) for patients who do not enter the DBTP; or 1 day before the first dose of DBTP (or the date of the first dose of the DB IP if the last scheduled assessment date in the OLTP is on the date of the first dose of the DBTP) for patients who enter the DBTP.

The DBTP starts with the first day of randomization and ends with the last scheduled assessment at Visit 26 (Week 44) or ET.

The SFU period starts one day after the end of the previous period and ends with the last available assessment. For patients without Visit 27 (Week 46) or Visit 28 (Week 48) assessment, the SFU period would not be derived.

Screen-failure patients (ie, patients screened but not included in the OL Safety Population) and the associated reasons for failure will be tabulated overall for the Screened Population.

The number and percentage of patients in the Screened, OL Safety and OL ITT Populations will be summarized overall and by study center. The number and percentage of patients in the Randomized, DB Safety, and DB ITT Populations will be summarized overall by treatment group and by treatment group and study center.

The number and percentage of patients in the OL Safety Population, who prematurely discontinued from the OLTP, who completed the OLTP, who entered the DBTP, and who entered the SFU period will be summarized overall and by reasons for premature discontinuation as recorded on the respective disposition pages of the electronic case report form (eCRF).

Similarly, the number and percentage of patients in the DB Safety Population who completed the DBTP, who prematurely discontinued from the DBTP, and who entered the SFU period will be summarized overall, by DB treatment group and by reasons for premature discontinuation as recorded on the respective disposition pages of the eCRF. Patients who relapse during the DBTP will also be summarized as completing the study.

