11.1 ADVERSE EVENTS

AEs will be coded by system organ class and preferred term using the *Medical Dictionary for Regulatory Activities* (MedDRA), Version 21.1 or newer.

An AE will be considered a treatment-emergent adverse event (TEAE) if the AE began or worsened (increased in severity or became serious) on or after the date of the first dose of OL IP. Per eCRF instructions, a new AE record will be created with a new AE onset date for any AE that worsens. Therefore, TEAEs can simply be identified as those AEs with recorded onset date (and time, if known) on or after the date of the first dose of IP.

The number and percentage of patients reporting TEAEs during the OLTP will be tabulated by system organ class and preferred term; by system organ class, preferred term, and severity; and by system organ class, preferred term, and relationship to IP.

The number and percentage of patients reporting TEAEs during the DBTP will be tabulated for each treatment group by system organ class and preferred term; by system organ class, preferred term, and severity; and by system organ class, preferred term, and relationship to IP. The total number and percentage of TEAEs during the DBTP will also be summarized by severity and relationship to IP for each treatment group.

The number and percentage of patients reporting TEAEs during the OL SFU period will be tabulated by system organ class and preferred term for the OL Safety Population. The number and percentage of patients reporting TEAEs during the DB SFU period will be tabulated by system organ class, preferred term, and DB treatment group for the DB Safety Population.

For OLTP, DBTP, or SFU period, if more than 1 AE was coded to the same preferred term for the same patient, the patient will be counted only once for that preferred term using the most severe and most related occurrence for the summarization by severity and by relationship to IP.

An AE that occurs more than 30 days after the date of the last dose of DB IP or occurs after the last SFU visit (whichever comes last) will not be summarized except for AEs related to reported pregnancies. AEs associated with pregnancies reported in the protocol-required timeframe up to approximately 12 weeks following the last dose of DB IP will be summarized.

The number and percentage of patients with common ($\geq 2\%$ of patients in any treatment group) TEAEs will be summarized by preferred term for OLTP and be summarized by preferred term and treatment group for DBTP.

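### Safety follow-up denominators are inconsistent across SAP 6.4, 7.1, 11.0 and 11.1, so follow-up percentages in the open-label and double-blind tables do not share a common meaning

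*SAP*

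**What the plan says.** - **Denominator rule.** SAP 11.0: summaries for the "OL SFU period or DB SFU period will use the OL SFU population or the DB safety population as the denominator". Protocol 7.3.4 names the same two populations.
- **OL SFU population.** Protocol 7.1.4: it "will consist of patients in the OL safety population who were not randomized". SAP 6.4 narrows this to patients "who were not randomized and completed at least one visit in the SFU period". SAP Appendix V notes that the definition was modified; SAP 17.0, which lists departures from the protocol, does not.
- **DB safety population.** SAP 6.6: "all patients in the randomized population who took at least 1 dose of DB IP". No SFU visit is required.
- **When an SFU period exists.** SAP 7.1: "For patients without Visit 27 (Week 46) or Visit 28 (Week 48) assessment, the SFU period would not be derived".
- **SFU adverse-event table.** SAP 11.1 has patients "reporting TEAEs during the OL SFU period will be tabulated by system organ class and preferred term for the OL Safety Population", and the DB SFU table on the DB Safety Population by arm. Protocol 7.3.4.1 puts the OL table on the OL safety follow-up population instead.
- **Other SFU tables.** Ocular events in SAP 11.1 use the OL SFU population and the DB safety population. SFU lens opacity in SAP 11.6 uses only patients who had that assessment.
- **What survives termination.** Appendix IV keeps OL and DB SFU summaries of adverse events overall, treatment-emergent events, ocular events and serious treatment-emergent events.

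**The concern.** A percentage describes risk during follow-up only if everyone in the denominator could have contributed an event. On the DB side the plan fails this test: a treated patient with no derived SFU period counts below the line and can never count above it. SAP 6.4 removes the same problem for open-label patients, with no DB counterpart.

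SAP 11.1 then contradicts 11.0 on the open-label side. The OL Safety Population includes randomized patients, whose SFU period follows double-blind treatment, so they cannot have an OL SFU event.

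At stake is how events after stopping drug are read. The OL and DB SFU percentages will stand in the same report and invite comparison, but they answer different questions, and the OL one depends on which SAP section the programmer follows.

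**Working it through.** The documents give no SFU event rate or attendance figure, so there is no stated result to reproduce. The planning counts used below come from SAP 14.0: 345 randomized, 115 per arm, 1035 entering open-label treatment. They are consistent with each other: 345 / 0.333 = 1036, against 1035 stated (345 x 3). They serve only as illustration, since the study was stopped early.

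**1. DB side.** Let N be an arm's DB safety patients, m the share with no derived SFU period, and x the number with an SFU event.

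- Printed: x / N
- Among patients followed: x / [N(1 - m)]
- Ratio of printed to followed: 1 - m

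Take N = 115 and a 10% rate among those followed. The values of m are assumptions.

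| m | With SFU period | Printed | Relative shortfall |
|---|---|---|---|
| 0 | 115 | 10.0% | 0 |
| 10% | 103.5 | 9.0% | 10% |
| 20% | 92 | 8.0% | 20% |
| 30% | 80.5 | 7.0% | 30% |

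If m differs between arms, equal rates look unequal. At m = 10% in one arm and 20% in another, a common 10% prints as 9.0% and 8.0%.

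**2. OL side.** Planned non-randomized patients: 1035 - 345 = 690. With a 10% rate among those with an SFU visit, the same events give:

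| m | With SFU visit | SAP 6.4 with 11.0 | Protocol 7.1.4 (690) | SAP 11.1 (1035) |
|---|---|---|---|---|
| 0 | 690 | 10.0% | 10.0% | 6.7% |
| 10% | 621 | 10.0% | 9.0% | 6.0% |
| 20% | 552 | 10.0% | 8.0% | 5.3% |
| 30% | 483 | 10.0% | 7.0% | 4.7% |

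The 6.7% is 69/1035 and needs no assumption about attendance.

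**3. Direction of the OL/DB contrast.** It depends on the table. At m = 10% on both sides, the ocular table sets OL 10.0% beside DB 9.0%. The adverse-event table as worded in 11.1 sets OL 6.0% beside DB 9.0%, so there the open-label figure is diluted more.

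**4. Two gaps in the period rule.**

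- The condition in SAP 7.1 can mean that both visits are missing or that either is. The second reading conflicts with the one-visit rule in 6.4 and makes m larger.
- SAP 7.1 ends the DB period at Visit 26 or early termination, while 11.1 keeps events up to at least 30 days after the last DB dose. In a patient with no SFU visit, an event between those points belongs to no defined period.

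**The case against.** - **All treated patients is a legitimate denominator.** It keeps the arms as treated, whereas restricting to attenders conditions on something that happens after treatment. This stands. Counting every treated patient and assigning events by date would also be coherent. The plan does not do that: it denies an SFU period to non-attenders and keeps them in the denominator.
- **The DB denominator follows the protocol.** Correct. A reader might infer that SAP 11.0 departs from the protocol here; it matches Protocol 7.3.4. The unlisted departure is the visit condition in SAP 6.4.
- **Readers can rescale.** SAP 7.1 already reports by arm how many DB safety patients entered SFU, and Appendix IV keeps disposition summaries. This stands for the DB tables and lowers the importance of the point. It does not settle 11.0 against 11.1.
- **Attendance may be high.** Protocol 8.8 expects patients who stop early to return for both SFU visits. It also lists loss to follow-up and withdrawal of consent as reasons for stopping, and SAP 6.4 and 7.1 provide for absent visits. Some loss is foreseen, but its size is not.
- **The scope is narrow.** Lens opacity already uses assessed patients, means of vital signs are untouched, and tables of serious treatment-emergent events appear only if five or more patients have them. All of this stands.
- **The 11.1 wording may be a slip.** Probably so, given Protocol 7.3.4.1, but as written it tells the programmer to use the wrong population.

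**Conclusion.** The point holds as a minor one: the SFU denominators are inconsistent and should be reconciled. The firmest part is the contradiction between SAP 11.0 and 11.1, which on planned counts turns a true 10% into about 6.7% at full attendance. On the DB side the printed figure is (1 - m) times the rate among followed patients: no effect at m = 0, and 10% to 30% relative for m from 10% to 30%.

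Three stronger readings are tempting and not supported:

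- That DB SFU rates are certainly understated, or by a particular amount. The documents give no attendance figure, and the 20% dropout in SAP 14.0 is not an SFU non-attendance rate.
- That placebo is distorted more because relapsing patients return less often. Nothing in the documents gives attendance by relapse status or by arm.
- That open-label figures are always the undiluted ones. For the adverse-event table in 11.1 the reverse holds.

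The primary analysis and its power are not affected.

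**What to change.** 1. In SAP 6, add a DB SFU population: DB safety patients with a derived SFU period, by treatment received, mirroring 6.4.
2. Use it as the denominator for DB SFU percentages in 11.0 and in the adverse-event and ocular-event tables of 11.1.
3. In 11.1, move OL SFU treatment-emergent events to the OL SFU population.
4. In 7.1, state that an SFU period is not derived only when neither Visit 27 nor Visit 28 took place.
5. For patients with no SFU visit, list separately by arm any event after Visit 26 or early termination and within the 30-day window. A death or serious event before Visit 27 is then not lost.
6. In 17.0, record the 6.4 definition as a departure from Protocol 7.1.4, and the new DB SFU denominator as a departure from Protocol 7.3.4.

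The cost is SAP wording, one population flag and one short listing. The small downside is that DB SFU percentages become conditional on attendance, which the by-arm counts of SFU entry already planned in 7.1 disclose.

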The use of placebo control is critical to the study design both to understand the safety findings of the drug and to ensure that efficacy results can be interpreted. In this study, the placebo control is used during the DB treatment period to demonstrate the reemergence of symptoms of schizophrenia upon withdrawal of cariprazine compared with patients who continue cariprazine treatment. Patients who continue cariprazine treatment should maintain improvement in their schizophrenia symptoms for a longer period of time when compared to those switched to placebo. Patients switched to placebo should have an earlier return of symptoms of schizophrenia.

The fixed-dose design during the DB treatment period was selected to maintain patients at the cariprazine dose level at which their symptoms of schizophrenia had responded. The dose selected, 4.5 mg/d, represents a dose that has been proven to be efficacious in schizophrenia while minimizing side effects. The lower dose during the DB treatment period was

determined following an FDA request to include doses lower than those used to achieve a response in the acute phase, while maintaining a dose within the approved range for that indication (1.5 to 6.0 mg/d). If both doses prove to be effective in preventing relapse, an evaluation will be made to see if a lower dose also achieves better tolerability during the maintenance phase of treatment.

The duration of the DB treatment period, with a maximum of 26 weeks, was selected to provide sufficient time to demonstrate schizophrenia relapse upon withdrawal of cariprazine. The 4-week safety follow-up (SFU) period allows continued patient monitoring after investigational product (IP) has been discontinued.

2 Study Objectives and Clinical Hypotheses

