7.3.4 Safety Analyses

The safety analyses will be performed for the OL safety, OL SFU, and DB safety populations. The summarization will be overall for the OL treatment period in the OL safety population and for the OL SFU period in the OL SFU population. The summarization will be by treatment group for the DB treatment period and DB SFU period in the DB safety population. The summarization for the OL treatment period will use the OL safety population as the denominator. The summarization for the DB treatment period will use the DB safety population as the denominator. The summarization for the OL SFU period and DB SFU period will use the OL SFU population and the DB safety population as the denominator, respectively.

Safety parameters will include AEs, clinical laboratory parameters, vital signs, ECG parameters, ophthalmological parameters, C-SSRS, and EPS scales (AIMS, BARS, and SAS).

For each safety parameter, the last assessment made before the first dose of OL IP will be used as the Baseline for all analyses of that safety parameter, unless stated otherwise.

The derived visits in the DB treatment period will use the same strategy as described for the additional efficacy endpoints. The detailed week mapping windows will be provided in the SAP.

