10.3 ADDITIONAL EFFICACY PARAMETERS

The additional efficacy parameters will include the following at scheduled postbaseline visits:

- Change from baseline in the PANSS total score
- Change from baseline in PANSS positive subscale score
- Change from baseline in PANSS negative subscale score
- Change from baseline in PANSS factor score for positive symptoms
- Change from baseline in PANSS factor score for negative symptoms
- Percentage response (PANSS improvement \geq 30%)
- Change from baseline in the CGI-S score
- Clinical Global Impressions—Improvement (CGI-I) score

- Change from baseline in the Brief Assessment of Cognition in Schizophrenia scale (BACS) individual subtest scores
- Change from baseline in BACS composite score Z score
- Change from baseline in the BACS composite T score
- Change from baseline in personal and social performance (PSP) score and sub-domain scores

For the continuous endpoints, the change from baseline refers to the change from OL baseline during the OLTP, and the change from DB baseline during the DBTP, unless stated otherwise. For CGI-I, the OL baseline CGI-S value will be used as the baseline variable.

Descriptive statistics for additional quantitative parameters will be provided by visit for the OL ITT population and the DB ITT population using both last-observation-carried forward (LOCF) and observed cases (OC) approaches. LOCF approach will be used to impute missing postbaseline values. Imputation of missing values will be done for the OLTP and the DBTP separately.

For the DBTP, the continuous variables (change from DB baseline) will be analyzed by using a mixed-effects model for repeated measures (MMRM) with treatment group, country, visit, and treatment group-by-visit interaction as fixed effects and the baseline value and baseline-by-visit interaction as the covariates. An unstructured covariance matrix will be used. The Kenward-Roger approximation ([Kenward and Roger, 1997](#)) will be used to estimate denominator degrees of freedom. The analysis will be performed based on post-DB baseline scores using only the OC without imputation of missing values. Least squares mean and their standard errors based on the MMRM analysis will be plotted by treatment group and visit.

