11.3 VITAL SIGNS

Descriptive statistics (n, mean, SD, minimum, median, and maximum) for vital signs (supine systolic and diastolic blood pressures, supine pulse rate, weight, BMI, waist circumference, and temperature) and changes from baseline values at each visit and at the end of study will be presented overall for the OLTP and OL SFU period, and by treatment group for the DBTP and DB SFU period.

Vital sign values will be considered as PCS if they meet both the observed-value criteria and the change-from-baseline criteria listed in [Table 11-4](#). The number and percentage of patients with PCS postbaseline values will be tabulated overall for the OLTP, and by treatment group for the DBTP. The percentages will be calculated relative to the number of patients with available baseline values and at least 1 postbaseline assessment for the corresponding periods (OLTP or DBTP). The numerator will be the total number of patients with available baseline values and at least 1 PCS postbaseline value for the corresponding periods (OLTP or DBTP). A supportive tabular display of patients with PCS postbaseline values will be provided, including the PID number, study center number, and baseline and all postbaseline (including non-PCS) values.

In addition, a tabular display showing all AEs that occurred in patients who had PCS postbaseline vital sign values will be provided.

The number and percentage of patients with orthostatic hypotension will be provided for OLTP and DBTP. Orthostatic hypotension is defined as a reduction of ≥ 20 mm Hg in systolic blood pressure or a reduction of ≥ 10 mm Hg in diastolic blood pressure while changing from the supine to standing position. A supportive listing of patients with orthostatic hypotension will be provided. A listing of all AEs for patients with orthostatic hypotension will also be provided.

Table 11-4 Criteria for Potentially Clinically Significant Vital Signs

Parameter	Flag	Criteria^a	
		Observed Value	Change From Baseline
Supine systolic blood pressure, mm Hg	High	≥ 180	Increase of ≥ 20
	Low	≤ 90	Decrease of ≥ 20
Supine diastolic blood pressure, mm Hg	High	≥ 105	Increase of ≥ 15
	Low	≤ 50	Decrease of ≥ 15
Supine pulse rate, bpm	High	≥ 120	Increase of ≥ 15
	Low	≤ 50	Decrease of ≥ 15
Weight, kg	High	—	Increase of ≥ 7%
	Low	—	Decrease of ≥ 7%

a A postbaseline value is considered potentially clinically significant if it meets both the observed-value and the change-from-baseline criteria.

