16.0 DATA HANDLING CONVENTIONS

16.1 VISIT TIME WINDOWS

Table 16-1 presents the visits assigned for efficacy and safety analyses and the corresponding range of treatment days (window) during which an actual visit may occur.

Table 16-1 Visit Time Windows

Derived Visit	Open-label Period	
	Scheduled Visit Day Relative to the first dose of OL IP	Window
OL Baseline	Day 1	Days \leq 1
OL Week 1	Day 8	Days [2, 11]
OL Week 2	Day 15	Days [12, 18]
OL Week 3	Day 22	Days [19, 25]
OL Week 4	Day 29	Days [26, 35]
OL Week 6	Day 43	Days [36, 49]
OL Week 8	Day 57	Days [50, 63]
OL Week 10	Day 71	Days [64, 77]
OL Week 12	Day 85	Days [78, 91]
OL Week 14	Day 99	Days [92, 105]
OL Week 16	Day 113	Days [106, 119]
OL Week 18	Day 127	120 \leq days \leq the day of the last visit during the OL period*
End of the OL Period ^a	Last Assessment during the OL	
Double-blind Period		
	Scheduled Visit Day Relative to the first dose of DB IP	Window
	Day 1	Days \leq 1
DB Baseline (for efficacy endpoints only)	Day 15	Days [2, 21]
DB Week 2	Day 29	Days [22, 35]
DB Week 4	Day 43	Days [36, 49]
DB Week 6	Day 57	Days [50, 63]
DB Week 8	Day 71	Days [64, 77]
DB Week 10	Day 85	Days [78, 91]
DB Week 12	Day 99	Days [92, 105]
DB Week 14	Day 113	Days [106, 119]

Derived Visit	Open-label Period	
	Scheduled Visit Day Relative to the first dose of OL IP	Window
DB Week 18	Day 127	Days [120, 133]
DB Week 20	Day 141	Days [134, 147]
DB Week 22	Day 155	Days [148, 161]
DB Week 24	Day 169	Days [162, 175]
DB Week 26	Day 183	176 ≤ days ≤ the day of the last visit during the DB period
End of the DB period^a	Final or Termination Visit during the double-blind treatment period	
	Safety-follow-up (SFU) Period^b	
	Scheduled Visit Day Relative to the start of SFU	Window
SFU Week 2 ^b	Day 15	+1 ≤ days ≤ 21
SFU Week 4 ^b	Final or Termination Visit of the study after day 21 .	

OL Day 1 = the date of the first dose of open-label investigational product;

DB Day 1 = the date of the first dose of double-blind investigational product. There is no Day 0.

a Presented in analysis tables for safety parameters, including but not limited to electrocardiograms, clinical laboratory values, and vital signs.

b Presented in analysis tables for vital signs.

OL = Open Label; DB = Double-blind; SFU = Safety Follow-up; ET = Early Termination; IP = Investigational Products.

* All the available OL week 18/visit 13 Ophthalmological examination will be mapped to the OL safety period.

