APPENDIX IV ANALYSES SPECIFIED FOR ABBREVIATED CSR

On 14 DEC 2020, FDA provided Type C Written Response in which they agreed to release Allergan of the postmarketing requirement (PMR 2947-9) to conduct Study RGH-MD-24, based on new information obtained since initial Vraylar approval in SEP 2015. Study RGH-MD-24 was thus early terminated. The analyses for the abbreviated CSR are the subset of analyses specified in the SAP and listed below. The details are provided in the corresponding SAP sections.

Patient disposition and analysis populations

- Summary of screen failure patients and the associated reasons for failure
- Summary of patient disposition during OLTP and DBTP respectively
- Summary of analysis populations

Demographics and other baseline characteristics

- Summary of demographic and other baseline characteristics, and baseline efficacy variables
- Summary of prior and concomitant medications

Efficacy analyses

- Primary efficacy analysis
- Analyses of change from baseline in the PANSS total score during OLTP and DBTP
- Analyses of change from baseline in BACS composite score

Extent of exposure

- Summary of exposure during OLTP, DBTP and entire study

Safety analyses

- Overall summary of AEs during OLTP, OL Safety Follow-up, DBTP, and DB Safety Follow-up
- Summary of TEAEs during OLTP, OL Safety Follow-up, DBTP, and DB Safety Follow-up

- Summary of treatment-related TEAEs during OLTP and DBTP
- Summary of TEAEs leading to premature discontinuation of IP during OLTP and DBTP
- Summary of ocular events during OLTP, OL Safety Follow-up, DBTP, and DB Safety Follow-up
- Summary of TESAEs during OLTP, OL Safety Follow-up, DBTP, and DB Safety Follow-up
- Summary of TESAEs of ocular events during OLTP and DBTP
- Summary of laboratory PCS during OLTP and DBTP
- Summary of CSSRS during OLTP and DBTP

The following listings will be provided for the abbreviated CSR

- Patients with TEAEs leading to premature discontinuation of IP
- AEs for patients with TEAEs leading to premature discontinuation of IP
- Patients with ocular events
- AEs for patients with ocular events
- Patients who died
- AEs for patients who died
- Patients with SAEs
- Patients with laboratory PCS during OLTP and DBTP
- Patients who meet potential Hy's law criteria during OLTP and DBTP
- Patients with suicidal ideation or behavior
- Patient disposition
- Patients who discontinued OLTP or DBTP
- Patients with protocol deviations

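### By-arm double-blind threshold and shift tables for safety use only the pre-open-label baseline, so they cannot separate abnormalities that start after randomisation from open-label effects that have not resolved

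*SAP*

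**What the plan says.** Protocol Section 7.3.4 and SAP Section 11.0 set the same default. The SAP's wording is: "the last assessment made before the first dose of OL IP will be used as the baseline for all analyses of that safety parameter". Both documents leave room for exceptions, but SAP Sections 11.1 to 11.7.1 make none. The first row of the DB block in SAP Table 16-1 is labelled "DB Baseline (for efficacy endpoints only", so no DB safety baseline exists. For efficacy the SAP does re-base: Section 10.3 uses "the change from DB baseline during the DBTP".

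The safety tables are nevertheless presented by randomised arm. For vital signs, SAP Section 11.3 says: "The number and percentage of patients with PCS postbaseline values will be tabulated overall for the OLTP, and by treatment group for the DBTP". Section 11.2 does the same for potentially clinically significant (PCS) laboratory values and for lipid and glucose shifts, Section 11.3 for hypertension shifts, and Section 11.4 for ECG PCS values. Section 11.0 makes by-arm DB summaries the general rule, which covers QTc increases (Section 11.4) and treatment-emergent parkinsonism and akathisia (Section 11.7.1).

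On purpose, Protocol Section 1 says that, if both doses prevent relapse, an "evaluation will be made to see if a lower dose also achieves better tolerability during the maintenance phase of treatment". After early termination, SAP Appendix IV keeps a subset of analyses, including "Summary of laboratory PCS during OLTP and DBTP".

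**The concern.** Randomisation is possible only from Week 14, so patients in all three arms enter the DB period already exposed to cariprazine. Judged against a value from before that exposure, a patient who gained 8% on open-label drug and then held that weight on placebo is a placebo case: in Table 11-4, weight has no observed-value criterion, only a change of 7% or more.

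Whether 3.0 mg/d is better tolerated than 4.5 mg/d in maintenance, or how either compares with placebo, is a question about what happens from randomisation onwards. A count that pools carried-over and new abnormalities does not answer it. A reader of the planned table cannot tell whether an arm's rate reflects abnormalities that began under the randomised treatment or earlier ones that did not go away.

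**Working it through.** **Inputs.** The plan states no figure for these tables, so there is none to reproduce. From the documents: the baseline rule (SAP 11.0, Protocol 7.3.4), the period limits on numerators (SAP 11.2 to 11.4), the visit schedule (Protocol Table 4, Section 6.5.5), and 115 planned patients per arm (SAP 14.0). All rates below are assumptions.

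**1. Threshold tables.** Let *c* be the share of each randomised arm already beyond a threshold at the end of the open-label period, *q* the share of those still beyond it at a DB visit, and *p* the new-onset rate among the rest. Assume resolved cases do not recur. With the pre-open-label baseline,

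rate = c·q + (1 − c)·p.

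With a DB baseline and a denominator of patients not yet meeting the criterion, rate = p.

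Take p = 4% (placebo) and 10% (drug).

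| Baseline and assumption | Placebo | Drug | Difference (points) | Ratio |
|---|---|---|---|---|
| DB baseline | 4.0% | 10.0% | 6.0 | 2.50 |
| Pre-open-label, c = 5%, q = 1 in both arms | 8.8% | 14.5% | 5.7 | 1.65 |
| Pre-open-label, c = 15%, q = 1 in both arms | 18.4% | 23.5% | 5.1 | 1.28 |
| Pre-open-label, c = 30%, q = 1 in both arms | 32.8% | 37.0% | 4.2 | 1.13 |
| Pre-open-label, c = 15%, q = 0.5 on placebo, 1 on drug | 10.9% | 23.5% | 12.6 | 2.16 |

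The c = 15% rows are 0.15 + 0.85 × 0.04 = 0.184; 0.15 + 0.85 × 0.10 = 0.235; and 0.15 × 0.5 + 0.034 = 0.109.

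In patients, at 115 per arm with c = 15% and q = 1, about 17.3 cases per arm are carried over (0.15 × 115). New onsets are 3.9 on placebo (0.85 × 115 × 0.04) and 9.8 on drug (0.85 × 115 × 0.10).

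**2. Direction.** The difference under the planned baseline is (1 − c)(p_drug − p_placebo) + c(q_drug − q_placebo). It equals the new-onset difference when q_drug − q_placebo = p_drug − p_placebo, here 6 points. With full persistence on drug, the contrast shrinks if more than 94% of carried-over cases persist on placebo and widens if fewer do.

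**3. Mean change.** Change from the open-label baseline = change from the DB baseline + (DB baseline − open-label baseline). The last term has the same expectation in every randomised arm, so the expected contrast among the same patients is unchanged. Only precision differs. With equal variances, the SD ratio is √[2(1 − r₁)] / √[2(1 − r₂)], where r₁ and r₂ are the correlations of the DB value with the open-label and DB baselines. At r₁ = 0.7 and r₂ = 0.9 it is √0.6 / √0.2 = 1.73; at 0.7 and 0.7 it is 1.00.

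**4. What counts as in the period.** For laboratory, vital-sign and ECG PCS tables, the abnormal value must fall in the DB period, so an abnormality that resolved before randomisation and stayed resolved is not counted. The extrapyramidal definitions in SAP 11.7.1 refer to any postbaseline assessment and name no period. Read literally, akathisia that had resolved before randomisation would still count. The QTc-increase count in Section 11.4 also names no period.

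**5. What survives early termination.** Among the affected tables, Appendix IV keeps laboratory PCS and its patient listing. Vital signs and ECG appear only as data listings. Extrapyramidal scales, QTc increases and lipid and glucose shifts are not on the list.

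**The case against.** **The effect on the contrast is not one-directional.** A reader might infer that the planned tables simply dilute the arm differences. That needs equal persistence across arms, which nothing in the documents establishes. Scheduled DB laboratory tests are at Visits 18, 22 and 26/ET, the first 10 weeks after Visit 13, and the only scheduled DB ECG is at Visit 26/ET. Abnormalities may have resolved on placebo by then, and the contrast then widens. This objection stands. It changes the description of the defect but does not remove it, because the table still cannot separate its two components.

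**Adverse events.** A reader might also infer that open-label adverse events are counted in every DB arm, because a treatment-emergent event is one that "began or worsened (increased in severity or became serious) on or after the date of the first dose of OL IP". The text does not support that. The DB tables cover events during the DB period, Section 11.1 identifies them by onset date, and a worsening gets a new record with a new date. What is missing is an explicit rule for an event that begins open-label and continues unchanged.

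**The pre-drug baseline is a legitimate choice.** Protocol and SAP state it consistently, and it suits a display of cumulative exposure. It also registers something that a DB-baseline table would lose. All randomised patients arrive on 4.5 mg/d, so any tolerability gain at 3.0 mg/d may appear partly as existing effects resolving, and a denominator restricted to unaffected patients drops exactly those patients. This stands, and it is why the DB-baseline tables should be added and not substituted.

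**Reach.** Safety is descriptive, the dose-tolerability evaluation is conditional on both doses working, and Protocol Section 1 does not name these tables as its basis. All of that is correct.

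**Conclusion.** The point holds for threshold and shift tables: laboratory PCS, lipid and glucose shifts, vital-sign PCS including weight change, hypertension shifts, ECG PCS and QTc increases, and treatment-emergent extrapyramidal symptoms. Judged only from the pre-open-label baseline, their by-arm DB counts combine persistence and new onset.

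The size depends wholly on assumed rates. With equal persistence, 15% carry-over takes a 6.0-point difference to 5.1, a loss of 15%; the ratio moves more, from 2.50 to 1.28. With faster resolution on placebo, the difference can exceed 6.0 points.

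Expected mean-change contrasts are unaffected. DB adverse event tables are not shown to be affected. No hypothesis test, Type I error rate or primary conclusion is touched. In the abbreviated report the practical reach is laboratory PCS. This is an inexpensive improvement to the descriptive safety evidence and not a flaw that invalidates it.

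**What to change.** - In SAP Sections 11.0 and 16.1, define a DB safety baseline as the last value before the first DB dose.
- Add by-arm DB threshold and shift tables on that baseline, among patients not already meeting the criterion at it.
- Keep the open-label-baseline tables and label them as the cumulative-exposure display, which also captures resolution of open-label effects.
- In Section 11.7.1, limit the DB extrapyramidal counts to assessments in the DB period; the same sentence would settle the QTc-increase count in Section 11.4.
- In Section 11.1, state how an adverse event that begins open-label and continues into the DB period is assigned.
- For the abbreviated report, add one DB-baseline laboratory PCS table to Appendix IV.

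No new data are needed: Protocol Section 8.4.4 already schedules laboratory tests, vital signs, extrapyramidal scales and ECG at Visit 13. The cost is more output, and two displays whose different denominators must be clearly labelled.
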